3. STATISTICAL CONSIDERATIONS

Data analysis will be performed according to [REDACTED] Standard Operating Procedures (SOPs).

The general analytical approach for all endpoints will be descriptive in nature
Unless otherwise stated, the following statistical approaches will be taken:

Continuous variables: Descriptive statistics will include the number of non-missing values, mean, standard deviation (SD), median, minimum, and maximum. The minimum and maximum values will be presented to the same number of decimal places as recorded in the raw data; mean and median will be presented to 1 decimal place more than raw data; and SD will be presented to two more decimal places than the raw data.

Categorical variables: Descriptive statistics will include frequency counts and percentages per category. Percentages will be rounded to one decimal place, with the denominator being the number of subjects in the relevant population with non-missing data.

Imputation: No imputation will be performed for missing data.

Confidence intervals (CIs): If required, CIs will be two sided and will use 95% confidence levels. Any analyses requiring significance testing will use a two-sided test at the 5% significance level.

Unscheduled visits: Unscheduled visits will be excluded from visit-based summary Tables, but will be included in data listings.

Early withdrawal visits Early withdrawal visits will be excluded from visit-based summary tables but will be included in data listings.

3.1 Data Capture

3.1.1 Database

The primary method of data collection is via the study database, developed within the chosen Electronic Data Capture (EDC) platform, IBM Clinical Development. The database has been designed based on the final protocol, the system/core configuration, electronic Case Report Form (eCRF) specifications and/or mock eCRF and consistency check specifications.

Data will be entered directly into the EDC system. Site-collected data will be entered directly from source notes at the site and will be verified by Clinical Research Associates (CRAs) to ensure data integrity.

Refer to the Data Management Plan for further details.

3.1.2 Third Party Data

3.1.2.1 Safety Laboratory

Central safety laboratory data will be received at [REDACTED] from PARC Clinical Research. This data transfer will occur once the central safety laboratory, SA Pathology, transfers the data to PARC as specified in the Data Transfer Specification. Data transfers are being processed at the end of each cohort throughout the study, with each transfer being reconciled against the CRF data.

The final data transfer(s) will be incorporated into the End of Study analysis once the final transfer has been received, reconciled and all issues are considered resolved.

No unit conversion of laboratory data is planned.

3.1.2.2 PK Laboratory

PK samples will be analyzed by HMS Trust Laboratory. PK analyses will be documented in a separate PK Analysis Plan and analyses will be performed by PKPD Systems. The PK Analysis Report will be incorporated directly into the appendices of the CSR.

3.1.2.3 PD Laboratory

PD samples will be analysed by collaborators selected by Lateral Pharma. Analysis of PD data will be considered outside the scope of this SAP.

3.2 Statistical Programming

3.2.1 Baseline

Baseline will be defined as the last available assessment prior to the first IMP administration. For part B, baseline will be assigned separately for the two treatment periods..

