Secondary endpoints	
Part A:
 
 
• Pharmacokinetic profile
 
 
Part B:
 
 
• Comparison of radicular “pain now” scores as peak change from baseline and area under the curve comparing the two arms over the full six hours
 
• Comparison of Patients general impression of change between dosing arms
 
• Adverse event rates in each dosing arm
 

Exploratory endpoints	
Part A:
 
 
• Pharmacodynamic assay and/or biomarkers of LAT8881 activity.
 
 
Part B:
 
 
• Mechanical QST assessment using Von Frey Aesthesiometer
 
• Evaluate the effect of Intravenous LAT8881, compared with placebo, on VAS radicular pain scores during straight-leg raise nerve stretch
 
• Bang Binding Index assessment, whereby participant will be asked to record which dosing occasion they believe they got the active IP.
 
• Pharmacodynamic assay and/or biomarkers of LAT8881 activity.
 

Study Design	
Part A:
 
This is a double-blind, randomized, placebo-controlled, single ascending dose study within 8 healthy volunteers of intravenous administration of LAT8881 over 5 minutes.
 
Part A of the Study will enrol 8 participants, each participant has three treatment days, 1 infusion per dosing day on days 1, 4 and 7 as well as two short visits for safety blood sampling on Day 3 and 6. The 8 subjects will be split into two groups of 4 subjects each (3 IMP and 1 placebo), with the two groups dosed a few days apart.
 
Participants arrive on the morning of treatment day, receive a single infusion, leave that afternoon (no overnight stay). Participants will be dosed at staggered intervals as determined by PI. .
 
Treatments are on Days 1 (0.8 mg/kg), Day 4 (1.2 mg/kg) and Day 7 (1.8 mg/kg) or placebo to allow sufficient washout and consideration of any safety observed following each dosing day. Day 3 and 6 safety blood results must be review prior dosing on the following day.
 
Participants will fast for 8 hours pre-dose and 4 hours post dose for each dosing occasion.

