## 3. SCHEDULE 1 OF OBSERVATIONS AND PROCEDURES PART A

Procedure	Day -30 to -2	Day 1/Day 4/Day 7 (hours)												Day 3/ 6	Day 14/ ETV
	Screening	Pre- Dose	Dose	5 min	0.25	0.5	1	1.5	2	2.5	3	4	6 Discharge	Day prior dosing 	+/- 2 day
Informed consent	x														
Medical history	x	x													
Inclusion/exclusion criteria	x														
Demography	x														
Physical examination, height, weight	x														
Symptom-directed physical exam		x											x		x
Pregnancy test (WOCBP) 	x	x													x
Urine drug screen, Urinalysis and Alcohol breath test 	x	x													
SARS-CoV-2 Test 															
HIV, Hepatitis B & C screening	x														
Clinical laboratory tests	x												x	x	
12-lead ECG	x	x							x				x		x
Vital signs	x	x			x	x	x	x	x	x	x	x	x		x
Spot pulse oximetry	x	x			x	x	x	x	x	x	x	x	x		x
Randomization		x													
Dose administration 			x												
AE review				x	x	x	x	x	x	x	x	x	x		x
Concomitant medication review	x	x	x	x	x	x	x	x	x	x	x	x	x		x
PK 		x		x	x	x	x	x	x			x	x		
PD 		x		x	x	x	x	x	x			x	x		
Discharge													x		

\*# Participants who withdraw early from the study will be encouraged to return to the clinic for an ETV assessment.

\* Participants may require an unscheduled visit to address safety issues and/or for any additional PK and/or PD sample collection as required.

1 All WOCBP will have a serum pregnancy test at Screening and at the ETV visit, if applicable. Urine pregnancy tests will be performed for WOCBP at all other specified subsequent visits. If a urine pregnancy test is positive, it must be confirmed by a serum pregnancy test.

2. Urine Drug Screen and Alcohol Breath Test will be performed in clinic. A urine dipstick will be completed at all visit. In the event of positive Leukocytes and/or nitrates that urine sample will be sent to the local labortaotry for a microscopic examination.

3. SARS-CoV-2 Test will be taken if clinically indicated and in line with local processes.  
 4. All participants will fast 8 hours prior and 4 hours after the study drug administration  
 5. Samples must be taken with enough time that results are available prior to planned IP dosing on the following morning.  
 6. Pre-dose, 5 ± 1 min, 15 ± 2 min, 30 ± 2 min, 60 ± 5 min, 2 h ± 10 min, 4h ± 20 min, 6h ± 30 min post-dose.

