2. PROJECT OVERVIEW

2.1 Study Design

This is a Proof-of-Concept study that consists of two parts

2.1.1 *Part A (single ascending dose study)*

Part A will be a double-blind, randomized, placebo-controlled, single ascending dose (SAD) study within 8 healthy volunteers of intravenous administration of LAT8881 over 5 minutes.

The SAD study will enrol 8 participants and each participant will have three treatment days, 1 infusion per dosing day on days 1, 4 and 7 as well as two short visits for safety blood sampling on

[figure not shown]
Day 3 and 6 (Figure 1). The 8 participants will be split into two groups of 4 participants each (3 IMP and 1 placebo), with the two groups dosed a few days apart.

Participants will arrive on the morning of each treatment day, receive a single infusion, leave that afternoon (no overnight stay). Participants on a given dosing day will be dosed at staggered intervals as determined by PI.

Treatments will be on Days 1 (0.8 mg/kg), Day 4 (1.2 mg/kg) and Day 7 (1.8 mg/kg) or placebo to allow sufficient washout and consideration of any safety observed following each dosing day. Day 3 and 6 safety blood results will be reviewed prior dosing on the following dosing day.

Participants will fast for 8 hours pre-dose and 4 hours post dose for each dosing occasion. Participants will be randomised, so on each treatment day per group, 3 participants receive LAT8881 and 1 receive placebo (different participants to receive placebo each treatment day). Participants will remain at the clinic until 6 hours post-infusion in order to collect blood samples for PK analysis and for review of safety and tolerability. Safety assessments will be reviewed in a clinic exit visit 7 days after the last infusion.

Figure 1: Part A Study Design

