2.4 Study Endpoints

2.4.1 Primary Endpoints

Part A

Safety and tolerability

- Incidence, severity, and causality of AEs
- Incidence and severity of clinical laboratory abnormalities
- Change from baseline in vital signs (blood pressure, temperature, respiratory rate, and heart rate)
- Change from baseline in 12-lead ECG parameters
- Incidence and severity of AEs

Part B

- The change in pain from baseline during and after each infusion on a VAS 0-10 numerical rating scale of “pain now” with measures taken as the infusion starts and at 15 minute intervals for the first hour, then every thirty minutes for an additional two hours, then hourly until 6 hours from infusion commencement

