3.2.2 Change from Baseline

Part A: $change from baseline = (postbaseline value) - (baseline value)$

Part B, Period 1:

$change from baseline = (postbaseline value) - (period 1 baseline value)$

$Percentage change from baseline = 100 \times change from baseline / (period 1 baseline value)$

$Mean change from baseline over 1-2 hours = [change from baseline at 1 hr + change from baseline at 1.5 hr + change from baseline at 2 hr] / 3$

$Mean change from baseline over 4-6 hours = [change from baseline at 4 hr + change from baseline at 6 hr] / 2$

Part B, Period 2:

$change from baseline = (postbaseline value) - (period 2 baseline value)$

$Percentage change from baseline = 100 \times change from baseline / (period 2 baseline value)$

$Mean change from baseline over 1-2 hours = [change from baseline at 1 hr + change from baseline at 1.5 hr + change from baseline at 2 hr] / 3$

$Mean change from baseline over 4-6 hours = [change from baseline at 4 hr + change from baseline at 6 hr] / 2$

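### Part A uses one pre-Day 1 baseline for three dosing days, so day-to-day shifts in vital signs and ECG are reported as change at the 1.2 and 1.8 mg/kg doses

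*SAP*

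**What the plan says.** SAP 3.2.1 sets the general rule: "Baseline will be defined as the last available assessment prior to the first IMP administration". It then makes one exception: "For part B, baseline will be assigned separately for the two treatment periods". SAP 3.2.2 follows the same pattern. Part B has one formula with a period 1 baseline and another with a period 2 baseline, while Part A has a single formula with no day or period index.

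Part A nevertheless has three dosing days per participant, and Protocol 7.1 describes it as a cross-over. The protocol synopsis ties dose to day: "Treatments are on Days 1 (0.8 mg/kg), Day 4 (1.2 mg/kg) and Day 7 (1.8 mg/kg) or placebo". On each day one participant per group of four has placebo, with "different participants to receive placebo each treatment day" (SAP 2.1.1). Protocol 21.1 and SAP 3.2.5 combine placebo from all three days into one column.

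The Part A primary endpoints in SAP 2.4.1 include change from baseline in vital signs and "Change from baseline in 12-lead ECG parameters". The Part A schedule (Protocol section 3) marks both in the pre-dose column of the block covering Days 1, 4 and 7. A same-day pre-dose value is therefore collected on each dosing day. Neither document says why it is not used as a baseline.

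**The concern.** A post-dose reading on Day 7 is compared with a reading taken six days and up to two active doses earlier. Whatever moved the participant's level in between is counted as change on the 1.8 mg/kg day. That could be familiarity with the clinic, ordinary day-to-day variation or a lasting effect of an earlier dose. Even a shift already present before the Day 4 infusion counts as change on the 1.2 mg/kg day.

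The comparator does not separate these sources. For active drug, dose and day are the same variable, and the pooled placebo column averages over the three days. A reader looking across the dose columns of a primary safety table could see a dose pattern that comes from the calendar, or miss a real one that the calendar offsets.

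**Working it through.** **Inputs.** Two groups of four, with three active and one placebo per group per day (SAP 2.1.1); dosing on Days 1, 4 and 7; a different placebo participant each day; placebo pooled (SAP 3.2.5); one Part A baseline (SAP 3.2.1, 3.2.2). The documents give no standard deviation or drift for any vital sign or ECG parameter.

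**1. Reproduce the allocation.** Per day: 2 × 3 = 6 active and 2 × 1 = 2 placebo, which matches Protocol 7.3. Over three days: 18 active + 6 placebo = 24 occasions.

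**2. Occasions measured against another day.** Days 4 and 7: 8 × 2 = 16 of 24, made up of 6 × 2 = 12 active and 2 × 2 = 4 placebo. The gaps are 4 − 1 = 3 days and 7 − 1 = 6 days.

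**3. Earlier active exposure on those 16 occasions.**
- Day 4 active: the 2 participants who had placebo on Day 1 are now active, so 6 − 2 = 4 of 6 have had an earlier active dose.
- Day 4 placebo: 2 of 2.
- Day 7 active: 6 of 6 (4 with one earlier active dose, 2 with two).
- Day 7 placebo: 2 of 2.
- Total: 4 + 2 + 6 + 2 = 14 of 16.

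**4. Additive drift, no drug effect.** Let the level rise by d per dosing visit, moving pre- and post-dose values equally within a day.

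| Column | Pre-Day 1 baseline | Same-day baseline |
|---|---|---|
| 0.8 mg/kg (Day 1) | 0 | 0 |
| 1.2 mg/kg (Day 4) | d | 0 |
| 1.8 mg/kg (Day 7) | 2d | 0 |
| Placebo, pooled | (2×0 + 2×d + 2×2d)/6 = d | 0 |

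For an assumed d of 1, 2 or 3 units, the spread from 0.8 to 1.8 mg/kg is 2, 4 or 6 units. A reader who compares each column with pooled placebo would see −d, 0 and +d.

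**5. What the single baseline contributes.** Four participants are active on both Day 1 and Day 7 (2 with placebo on Day 4 and 2 who never have placebo). In their 1.8 minus 0.8 mg/kg difference the shared baseline cancels. What remains is the raw Day 7 minus Day 1 difference, with no baseline adjustment.

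**6. A different shape of shift.** Suppose only the Day 1 pre-dose value is raised, by a, and everything afterwards is level. The pre-Day 1 baseline gives −a, −a, −a for the three doses and −a for pooled placebo, so there is no false trend. Same-day baselines give −a, 0, 0, which is a false pattern. Neither baseline is safe alone.

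**7. Illustration under assumed variability.** The assumed SDs are 8 between subjects, 4 between days and 4 for measurement; none comes from the documents. In 20,000 simulated trials per setting with no drug effect, the table shows how often the means rose across the three doses with a spread of at least 5 units.

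| d per visit | Pre-Day 1 baseline | Same-day baseline |
|---|---|---|
| 0 | 6% | 5% |
| 1 | 14% | 4% |
| 2 | 29% | 5% |
| 3 | 47% | 5% |

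**The case against.** The case for leaving the SAP alone has several sound parts.

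- **The shift can be seen.** SAP 12.4.2 and 12.7.2 tabulate observed values as well as change at each scheduled visit and timepoint. A Day 4 or Day 7 pre-dose shift is therefore visible, and with complete data the mean same-day change follows by subtraction. Its standard deviation does not. This limits the harm, but the endpoint itself still carries the shift.
- **No placebo-adjusted contrast is planned for Part A.** The −d, 0, +d pattern is what a reader would form by eye, not a planned output.
- **A pre-exposure baseline is legitimate.** The same people receive successive doses within a week, and a same-day baseline would subtract any persisting effect. This stands, and is why the pre-Day 1 version should be kept.
- **A same-day baseline is no cure-all.** Step 6 shows a shift for which it does worse. It also leaves the dose-day confounding in place, because that belongs to the escalation design.

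A reader might infer that the Part B dose rests on a faulty analysis. The documents do not support that. The dose is already stated in Protocol section 11 and SAP 3.2.6, and this SAP was written after 14 Part B participants had completed (SAP 2.5). The maximum tolerated dose rule in Protocol 7.3 counts dose-limiting toxicities, and the halting rules in Protocol 17.2 rest on adverse events. Neither uses mean change in vital signs or ECG.

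A reader might also want the same change for laboratory tests. That would be unsound. The schedule has no pre-dose laboratory sample on Part A dosing days. The Day 3 and Day 6 samples follow earlier doses, so a delayed rise would become the next dose's baseline. The age of the baseline would also differ by dose: one day for the later doses, but back to Screening for the first.

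**Conclusion.** The concern holds for vital signs and ECG in Part A. The 16 of 24 occasions measured against another day, and the 14 of those 16 that follow an earlier active dose, come directly from the design. The 0, d, 2d pattern follows if the shift is additive and common to pre- and post-dose values. Its size cannot be stated, because neither document gives d or any variability, and the figures for d of 1 to 3 units are illustrations. Drift is the firmer route. Carry-over is weaker, since the dosing interval is meant to allow washout. SAP 2.5 reports that pre-dose pain on Day 2 of Part B may have been lowered by time in the clinic. That is a different measure in a different population, so it shows only that pre-dose levels in this trial need not be stable.

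The consequence is a primary safety summary that can misattribute day effects to dose in the study report. It is not an inflated test error rate, because Part A is descriptive, and it is not evidence of a wrong dose decision.

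**What to change.** In SAP 3.2.1 and 3.2.2, for Part A vital signs and 12-lead ECG only:

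- Define a baseline for each dosing day as the last value before that day's infusion, and tabulate change from it.
- Keep change from the pre-Day 1 value beside it, to show cumulative or persisting effects. Word it as the value before the Day 1 infusion, whether active or placebo. SAP 2.1.1 sometimes uses IMP for active drug only, which leaves the baseline unclear for the two participants on placebo that day.
- Show placebo by day as well as pooled.
- State that a same-day baseline removes only shifts common to pre- and post-dose values and does not undo the confounding of dose with day.

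Leave the laboratory baseline and the maximum-shift tables unchanged.

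The cost is SAP wording, one more derivation and one more table set. No new data are needed. With two placebo participants per day, the by-day placebo columns will be sparse and serve only as a visual check.

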3.2.2 Change from Baseline

Part A: $change from baseline = (postbaseline value) - (baseline value)$

Part B, Period 1:

$change from baseline = (postbaseline value) - (period 1 baseline value)$

$Percentage change from baseline = 100 \times change from baseline / (period 1 baseline value)$

$Mean change from baseline over 1-2 hours = [change from baseline at 1 hr + change from baseline at 1.5 hr + change from baseline at 2 hr] / 3$

$Mean change from baseline over 4-6 hours = [change from baseline at 4 hr + change from baseline at 6 hr] / 2$

Part B, Period 2:

$change from baseline = (postbaseline value) - (period 2 baseline value)$

$Percentage change from baseline = 100 \times change from baseline / (period 2 baseline value)$

$Mean change from baseline over 1-2 hours = [change from baseline at 1 hr + change from baseline at 1.5 hr + change from baseline at 2 hr] / 3$

$Mean change from baseline over 4-6 hours = [change from baseline at 4 hr + change from baseline at 6 hr] / 2$

3.2.3 Study Day

Part A: Study Day will be derived as the number of days relative to date of first administration of study drug, where the day of first administration = 1.

Part B: Study Day will be number of days relative to date of administration of study drug for each period, where the day of administration = 1.

3.2.4 Listings, Tables and Figures

Listings, tables and figures will be delivered as individual .rtf files in accordance with the mock listings, tables and figures, with separate sets of outputs for each study part.

Data listings will present all data, with subjects grouped by treatment regimen (part A) or treatment sequence (part B).

3.2.5 Treatment groups – Part A

Tabulations will summarize data by treatment group, the pooling of all the study drug, and total (all groups). All placebo participants will be grouped in a single cohort for tabulation summaries.

For Part A, treatment groups within tables are planned to be presented as:

LAT8881 (0.8mg/kg) (N=X)	LAT8881 (1.2mg/kg) (N=X)	LAT8881 (1.8mg/kg) (N=X)	LAT8881 (All Doses) (N=X)	Placebo (N=X)	Total (N=X)
--------------------------------	--------------------------------	--------------------------------	---------------------------------	------------------	----------------

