2.2 Sample Size

No formal statistical sample size estimation has been performed due to the exploratory nature of this study. The sample size is based on clinical and practical considerations.

For Part A, a total of 8 participants will be dosed on each of three occasions with an increased dose (6 subjects) or placebo (2 subjects). It is expected that the sample size of 8 subjects (split into two groups of 4 subjects each (3 IMP and 1 placebo), with the two groups dosed a few days apart) should be adequate for evaluation of safety, tolerability, PK and PD parameters in this SAD study.

For Part B, a proof-of-concept, up to 20 participants, based on the PI's experience from design and management of lumbar radicular pain subjects, will be enrolled. It is expected that the sample size (10 participants receiving active drug then placebo and 10 receiving placebo then active drug) should be adequate for evaluation of safety and efficacy.

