12.1 Adverse Events (AEs)

AEs will be coded using the current version of the Medical Dictionary for Regulatory Activities (MedDRA, version 24.1) by system organ class (SOC) and preferred term (PT), classified from verbatim terms.

All AEs recorded during the study will be listed, grouped by participant and treatment group.

A Treatment Emergent Adverse Event (TEAE) is defined as any untoward medical occurrence reported or observed after the start of dosing with study drug and prior to the End of Study visit. Conditions present before the first dose of study drug that increase in severity after the first study drug administration will also be considered TEAEs. Where an AE start date is partially or fully missing, and it is unclear as to whether the AE started after treatment administration, it will be assumed to be a TEAE.

AE summaries will be restricted to TEAEs only.

An overview summary table of TEAEs will be provided for:

- Part A by treatment group and overall
- Part B by treatment within sequence, by treatment and overall

Table will include number of participants reporting at least one of the following:

- TEAE
- Grade 3+ TEAE
- Related TEAE
- Serious TEAE
- Serious and related TEAE

Number of participants discontinued from treatment due to a TEAE

Number of participants withdrawn from the study due to a TEAE

Number of deaths

For the TEAE summaries, participants who experience the same TEAE more than once will be counted only once for that event within each category (PT, SOC or overall).

The number and percentage of participants experiencing a TEAE, will be summarised for each SOC and PT by cohort and overall for the following categories of events, by severity:

- All TEAEs
- All TEAEs related to the study drug
- All Grade 3+ TEAEs
- All serious TEAEs
- All serious TEAEs related to the study drug

The number and percentage of participants experiencing a TEAE will be summarised for each SOC and PT by maximum severity and cohort for all TEAEs and all TEAEs related to study medication. If a participant experiences the same AE at more than one severity grade, the most severe rating or the stronger causal relationship to investigational product will be given precedence. Only severities that are populated will be reported.

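### Part A's pooled LAT8881 column counts each participant once over two or three active infusions against one placebo infusion, so its adverse-event incidence is expected to exceed placebo even for an inert drug

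*SAP*

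**What the plan says.** SAP 2.1.1 sets up Part A as a rotation within participants: "The SAD study will enrol 8 participants and each participant will have three treatment days". On each day, in each group of four, "3 participants receive LAT8881 and 1 receive placebo (different participants to receive placebo each treatment day". SAP 2.2 gives the totals per occasion: the 8 participants are "dosed on each of three occasions with an increased dose (6 subjects) or placebo (2 subjects".

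SAP 3.2.5 sets the Part A table columns: "Tabulations will summarize data by treatment group, the pooling of all the study drug, and total (all groups". It lays these out as three single-dose columns, a pooled active column (All Doses), one placebo column and a total. On placebo it says: "All placebo participants will be grouped in a single cohort for tabulation summaries".

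SAP 12.1 sets the counting rule: "participants who experience the same TEAE more than once will be counted only once for that event within each category (PT, SOC or overall". SAP 3 makes the number of subjects the denominator of percentages. SAP 8.1.2 summarises exposure separately. Neither document plans a per-infusion or exposure-adjusted adverse-event rate.

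Protocol 21.3.2 lists the Part A adverse-event summary by dose, with placebo combined, and overall. It names no pooled active column. SAP 2.5, which lists changes from the protocol, says that its changes concern Part B only.

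**The concern.** The pooled and placebo columns stand in the same table with the same kind of percentage, but a person in the pooled column has had two or three opportunities for an event and a person in the placebo column has had one. The share of people with at least one event rises with the number of opportunities, whatever was infused.

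The incidence of adverse events is a Part A primary endpoint (SAP 2.4.1). Part A is descriptive, so the displayed percentages are the result and no model corrects them. A reader who sets the pooled column against placebo could take part or all of a counting artefact for poorer tolerability.

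**Working it through.** **1. Reproduce the allocation.** Two groups, each with 3 active and 1 placebo per day, give 2 × 3 = 6 active and 2 × 1 = 2 placebo per occasion. This matches SAP 2.2.

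**2. Infusions per person.** In a group of four, three different people take placebo, one on each day. All 24 possible orders give active-infusion counts of 2, 2, 2 and 3. Over both groups, for completers:
- 6 people have 2 active and 1 placebo infusion, and 2 people have 3 active infusions.
- Active: 6 × 2 + 2 × 3 = 18 infusions in 8 people, mean 18/8 = 2.25.
- Placebo: 6 × 1 = 6 infusions in 6 people, mean 1.
- Check: 18 + 6 = 24 = 8 × 3.

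**3. Expected incidence for an inert drug, infusions independent.** Let p be the risk of at least one event after an infusion, the same on drug and placebo. The documents give no p, so a range is shown.

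Pooled incidence = [6(1 − (1 − p)²) + 2(1 − (1 − p)³)] / 8; placebo incidence = p.

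At p = 0.10: (6 × 0.19 + 2 × 0.271)/8 = 1.682/8 = 0.210.

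| p | All Doses | Placebo | Ratio | Expected people with an event |
|---|---|---|---|---|
| 0.05 | 10.9% | 5% | 2.18 | 0.87 of 8 vs 0.3 of 6 |
| 0.10 | 21.0% | 10% | 2.10 | 1.68 of 8 vs 0.6 of 6 |
| 0.20 | 39.2% | 20% | 1.96 | 3.14 of 8 vs 1.2 of 6 |
| 0.30 | 54.7% | 30% | 1.82 | 4.37 of 8 vs 1.8 of 6 |
| 0.50 | 78.1% | 50% | 1.56 | 6.25 of 8 vs 3.0 of 6 |

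For rare events the ratio approaches 2.25.

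**4. Events that cluster within people.** With a beta-binomial model of within-person correlation ρ, put s = (1 − ρ)/ρ, a = ps and b = (1 − p)s. The chance of at least one event in n infusions is 1 − B(a, b + n)/B(a, b), where B is the beta function. Ratio of pooled to placebo:

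| ρ | p = 0.05 | p = 0.10 | p = 0.20 | p = 0.30 |
|---|---|---|---|---|
| 0.2 | 1.91 | 1.86 | 1.75 | 1.65 |
| 0.5 | 1.55 | 1.52 | 1.46 | 1.40 |

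The ratio stays above 1 unless clustering is complete.

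**5. Unequal follow-up windows.** Dosing on Days 1, 4 and 7 with the exit visit on Day 14 gives windows of 3, 3 and 7 days. With a constant daily event rate of 0.01 to 0.10 (assumed), the ratio runs from 2.19 down to 1.79.

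**6. After the fix.** The expected share of infusions followed by an event is 18p/18 = p on active and 6p/6 = p on placebo, a ratio of 1.0 at every p. Within-person correlation does not change these expectations. Because every dosing day is split 6 to 2, the comparison is also balanced for day and follow-up window.

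**The case against.** No decision rests on this column. The maximum tolerated dose is judged per dose level (protocol 7.3), the stopping criteria are triggered by individual events (protocol 17.2), and no pooled-versus-placebo test is planned. Each single-dose column has one infusion per person and can be read fairly against placebo in the same table. The pooled percentage is itself a legitimate quantity, namely the share of people with any event over all their active dosing; what it lacks is a label. The distortion overstates adverse events and does not hide them. The mock tables are not in the documents, so a clarifying footnote may already exist.

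Most of this stands, and it limits the weight of the point. It does not remove it: the SAP text sets two percentages side by side that are not comparable, for a primary endpoint, and gives no instruction to say so.

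A reader might infer that an inert drug will always show about twice the placebo rate. The documents do not support that. It needs independent infusions and a modest event risk. The ratio is 1.56 at a risk of 50%, which may be nearer the truth for a row such as any event, and 1.40 to 1.55 with correlation 0.5 at risks of 5% to 30%. These are also ratios of expected values: at a 10% risk with independence, the placebo column is empty with probability 0.9⁶ = 53%. The counts hold for completers; withdrawal and replacement (protocol 17.1) can alter them.

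A reader might also infer that dose selection or a formal test is biased. Neither follows, because neither uses the pooled column.

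**Conclusion.** The point holds as a flaw in a descriptive display. The 18-in-8 against 6-in-6 imbalance follows from the documents alone, for completers, and with participant counting it raises the expected pooled incidence above placebo when the per-infusion risks are equal.

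The size rests on assumptions: about 1.8 to 2.2 times for independent infusions at risks of 5% to 30%, and about 1.4 to 1.9 times over the same risks with within-person correlation of 0.2 to 0.5. It is worth correcting because it concerns a primary endpoint and the correction needs no new data.

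**What to change.** In SAP 3.2.5 and 12.1, for all Part A TEAE tables:
- Keep the participant counts that protocol 21.3.2 calls for, and show the number of infusions in each column header.
- For the pooled and placebo columns, add the number and percentage of infusions followed by at least one TEAE (out of 18 and out of 6 if all complete). Note that the 18 infusions come from 8 people and are not 18 independent observations.
- Assign each Part A event to the most recent infusion before its onset. SAP 3.2.6 already does this for Part B; no rule is written for Part A, although the single-dose columns need one too.
- Footnote that Total covers three infusions per person.

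Alternatively, drop the pooled column, which matches the layout in protocol 21.3.2.

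Cost: several table shells change (the overview, the SOC and PT tables, and the maximum-severity tables). The change would also be late. SAP 2.5 describes an interim analysis after 14 Part B completers, and protocol 7.1 has the Part A safety data collated before Part B. The report should therefore say that it was made after Part A data were available; SAP 14 already provides for describing and justifying such changes.
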